TRUTH – TRU-cut biopsy in Tumor cHaracterisation

FIRST FACULTY
OF MEDICINE
Charles University

Version: 2.0
Date: 1-JAN-2024
Sponsor: General University Hospital in Prague
Main investigator: [name]
Co-investigator: [name]

Contact address: [name]
[name]
Czech Republic
[contact]
e-mail: [contact]
Trial chairs: [name]
[name]
[name]
Biostatistician: [name]
Study coordinator: [name]
Study design: Prospective cohort

DECLARATION OF THE MAIN INVESTIGATOR

Title: A single arm, prospective, cohort study to evaluate the feasibility of a complex classification of pelvic and abdominal tumors by tru-cut biopsy with immunohistochemistry, next-generation sequencing, and immunological examination.

Acronym: TRUTH

Protocol version: 2.0

The undersigned confirms that the above-referenced protocol has been acknowledged and accepted, he agrees to conduct the study in compliance with the approved protocol, and will adhere to the ICH guidelines, the most recent version of the Declaration of Helsinki, the EU General Data Protection Regulation 2016/679 (GDPR), relevant Czech laws implementing the GDPR, and any other regulatory requirements and Standard Operating Procedures (SOPs), as applicable.

The undersigned agrees not to disclose the confidential information contained in this document for any purpose other than the evaluation or conduct of the study, without prior written consent from the sponsor.

[figure not shown]
Center: Department of Obstetrics and Gynecology

General University Hospital and First Faculty of Medicine Charles University
Prague

Main investigator: [name]

Date: 1-JAN-2024

Signature:

A handwritten signature in blue ink that reads "[name]". The signature is written in a cursive, fluid style.

SYNOPSIS

Title	A prospective study to evaluate the feasibility of a complex classification of pelvic and abdominal tumors by tru-cut biopsy with immunohistochemistry, next-generation sequencing, and immunological examination.
Acronym	TRUTH
Type	Prospective cohort
Objective	The objective of this prospective study is to evaluate if a complex classification of pelvic and abdominal tumors using tissue samples obtained by tru-cut biopsy (TCB) is feasible.
Primary endpoint	The primary endpoint is the adequacy of samples obtained by TCB for histopathological examination.
Secondary endpoint	The secondary endpoints are the adequacy of samples obtained by TCB for: 
 1. next-generation sequencing examination 2. immunohistochemistry examination 3. immunologic examination
Additional endpoints	
 1. To evaluate which factors affect the primary and secondary endpoints, including: 
 a. tumor origin b. size of the tumor c. presence of ascites d. body mass index (BMI) e. biopsy site f. biopsy approach (transvaginal, transrectal vs. transabdominal) g. disease status – first diagnosis, recurrence or progression h. previous treatment modality – chemotherapy, anti-angiogenic therapy, PARP inhibitor therapy, hormonal therapy, or radiotherapy 2. To evaluate the overall safety of TCB 3. To evaluate the overall accuracy of TCB for complex classification of pelvic and abdominal tumors
Inclusion criteria	
 1. Presence of a pelvic/abdominal lesion with suspicion of malignancy: 
 a. new diagnosis of a presumed gynecologic tumor b. suspicious recurrence or progression of a known gynecologic malignancy c. pelvic/abdominal spread or recurrence of a non-gynecologic tumor (primary tumor or metastasis) d. pelvic/abdominal spread of a tumor of unknown origin 2. Age ≥ 18 years 3. Eastern Cooperative Oncology Group (ECOG) performance status grade < 3 4. Not pregnant

	5. Signed informed consent form
Exclusion criteria	1. Considered by the investigator to be unsuitable for any treatment 2. Early stage disease 3. Age <18 years
Time frame and sample size	A total of 250 consecutive patients Start date: 1-FEB-2024 End date: 31-JAN-2026

TABLE OF CONTENTS

DECLARATION OF THE MAIN INVESTIGATOR	2
SYNOPSIS	3
TABLE OF CONTENTS	5
LIST OF ABBREVIATIONS	6
ROLES AND RESPONSIBILITIES	7
1. BACKGROUND AND RATIONALE	8
2. ENDPOINTS	9
3. INCLUSION CRITERIA	10
4. EXCLUSION CRITERIA	10
5. STUDY DESCRIPTION	11
6. STATISTICAL ANALYSIS	18
7. STUDY TIMELINE AND SAMPLE SIZE	18
8. EXPECTED OUTCOMES	19
9. ETHICAL COMMITTEE APPROVAL	19
10. DATA HANDLING AND MONITORING	20
11. FUNDING AND SUPPORT	20
12. PUBLICATION PLAN	20
13. REFERENCES	21
APPENDICES	23

LIST OF ABBREVIATIONS

ADNEX	Assessment of Different NEoplasias in the adneXa (model)
AE	Adverse Events
BMI	Body Mass Index
BOT	Border-line Ovarian Tumor
CT	Computed Tomography
ECOG PS	Eastern Cooperative Oncology Group Performance Status
EC	Ethical Committee
FNAB	Fine Needle Aspiration Biopsy
GCP	Good Clinical Practice
HGSC	High Grade Serous Carcinoma
ICF	Informed Consent Form
IHC	Immunohistochemistry
ICH	International Conference on Harmonisation
LGSC	Low Grade Serous Carcinoma
LMWH	Low Molecular Weight Heparin
MI	Main Investigator
MRI	Magnetic Resonance Imaging
NACT	Neoadjuvant Chemotherapy
NGS	Next-Generation Sequencing
NOAC	New Anticoagulants
PI	Principal Investigator
PARP	Poly-ADP Ribose Polymerase
PET	Positron Emission Tomography
REDCap	Research Electronic Data Capture
TAS	Transabdominal Ultrasound
TCB	Tru-cut Biopsy
TIL	Tumor Infiltrating Lymphocytes
TMB	Tumor Mutational Burden
TVS	Transvaginal Ultrasound
US	Ultrasound

ROLES AND RESPONSIBILITIES

The principal investigator (PI) is responsible for the conduct of the study at his/her participating site, and for protecting the rights, safety, and well-being of all participants. As such, the PI must ensure adequate supervision of the study at the local site. If any tasks are delegated, the PI will maintain a log of appropriately qualified persons to whom he/she has delegated the specified study-related duties. The PI will ensure that adequate training is provided and documented for all study staff, before they conduct the assigned activities. Even when certain activities are delegated, the PI will ultimately remain responsible for the conduct of the study.

The main investigator's (MI) responsibility is to supervise the general conduct of the study, including study progress, communications, protocol training and support of the participating sites, annual reporting to the ethical committee (EC), end of study notification(s), and reporting of the results. The MI fulfils both investigator and sponsor responsibilities, as outlined in the International Conference on Harmonisation – good clinical practice (ICH-GCP) and applicable regulations.

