2.2. Secondary endpoint

The secondary endpoint is the adequacy of samples obtained by TCB for next generation sequencing, immunohistochemistry, and immunologic examination.

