2.3. Additional endpoints

1. To evaluate which factors affect the primary and secondary endpoint, including:
 - a. tumor origin
 - b. size of the tumor
 - c. presence of ascites
 - d. body mass index (BMI)
 - e. biopsy site
 - f. biopsy approach transvaginal, transrectal vs. transabdominal
 - g. disease status – the first diagnosis, the first and other recurrence or progression
 - h. previous treatment modality – chemotherapy, anti-angiogenic therapy, PARP inhibitor therapy, hormonal therapy, or radiotherapy
2. To evaluate the overall safety of TCB
3. To evaluate the overall accuracy of TCB for complex classification of pelvic and abdominal tumors

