2.4. Definitions of endpoints

The feasibility of TCB will be calculated as the proportion of patients in whom TCB was performed among all patients enrolled in the study.

Adequacy is defined as the proportion of patients in whom an adequate sample was obtained for a particular examination from among those patients who underwent TCB.

Accuracy will only be evaluated in patients in whom an adequate sample was obtained by TCB who underwent surgery with biopsy. Accuracy is defined as the concordance between the examination of samples obtained by TCB and the results of surgery with TCB to the final histopathology. The outcome of the final histopathological examination will be considered the reference standard.

For accuracy and adequacy, the impact of selected variables (e.g., approach, number of biopsies, and target lesion size) will be assessed in a multivariable analysis.

Safety is defined as the rate of complications related to TCB, including events occurring during the procedure, events within 24 hours after the procedure (early events), and events within 30 days of the procedure (late events).

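### No endpoint counts the patients whose biopsy was adequate for histopathology, IHC, NGS and immunology together, although the title and objective concern the feasibility of this complex classification

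*Protocol*

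**What the plan says.** The Synopsis sets the study to "evaluate if a complex classification of pelvic and abdominal tumors using tissue samples obtained by tru-cut biopsy (TCB) is feasible". The title names the components: tru-cut biopsy with IHC, NGS and immunological examination.

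The endpoints are these:

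- Primary (Synopsis; section 2.1 is similar): "The primary endpoint is the adequacy of samples obtained by TCB for histopathological examination".
- Secondary (section 2.2): "The secondary endpoint is the adequacy of samples obtained by TCB for next generation sequencing, immunohistochemistry, and immunologic examination". The Synopsis lists the same three examinations as separate numbered items.
- Additional (section 2.3): factors that affect the primary and secondary endpoints, safety, and one item that names complex classification: "To evaluate the overall accuracy of TCB for complex classification of pelvic and abdominal tumors".

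Section 2.4 defines adequacy as "the proportion of patients in whom an adequate sample was obtained for a particular examination from among those patients who underwent TCB". It then defines the word used in the title and objective: "The feasibility of TCB will be calculated as the proportion of patients in whom TCB was performed among all patients enrolled in the study". On accuracy it adds: "Accuracy will only be evaluated in patients in whom an adequate sample was obtained by TCB who underwent surgery with biopsy", with final histopathology as the reference standard.

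**The concern.** The question concerns a combined work-up, while the primary and secondary endpoints describe its parts one at a time. Under section 2.4 a patient whose tissue failed every examination still counts towards feasibility, because the biopsy was performed. The primary endpoint covers the part that is best known: section 1 reports an adequate sample in more than 93% of cases in the site's earlier retrospective study.

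The report could therefore show four fairly high adequacy rates and a high feasibility rate, and conclude that complex classification is feasible, without stating in how many patients it was achieved. Section 4.2.4 makes the gap relevant. Immunology comes after IHC and NGS, so it depends on the tissue that they leave.

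A joint rate chosen after the results are known is also open to selective definition, above all over how to treat patients in whom an examination was never requested.

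**Working it through.** **1. Does any endpoint give the joint rate?** Going through section 2:

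- Primary: histopathology only.
- Secondary: the singular noun in section 2.2 might suggest one combined measure, but the Synopsis list and the per-examination definition in section 2.4 show three separate rates.
- Feasibility: biopsied divided by enrolled. No examination result enters it.
- Accuracy: restricted to operated patients who already have an adequate sample, and judged against final histopathology. It conditions on adequacy and leaves out patients without surgery.
- Safety and predictive factors: different questions.

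None gives it.

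**2. Is there a planned figure to reproduce?** Not for the joint rate. The only related figure is in section 5: at least 250 patients, expected adequacy 70–90%, 95% confidence interval (CI) of at most 10%, calculated for histopathology alone. That figure is used in step 5.

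**3. Do the separate rates fix the joint rate?** The documents give no expected rate for each examination, so the inputs are assumptions. The figure of 93% follows section 1, and 70–90% is the range in section 5.

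Let p1 to p4 be the rates for histology, IHC, NGS and immunology, all over patients who underwent TCB.

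- Upper bound: the smallest of the four.
- Lower bound with no assumption (Fréchet): max(0, p1+p2+p3+p4 − 3).
- Lower bound if a sample inadequate for histology is inadequate for the rest: p1 − (p1−p2) − (p1−p3) − (p1−p4) = p2+p3+p4 − 2·p1 (or 0 if negative).
- Independence, for reference: p1·p2·p3·p4.

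For 93/90/80/70%:

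- no assumption: 0.93+0.90+0.80+0.70 − 3 = 0.33
- nested in histology: 0.93 − 0.03 − 0.13 − 0.23 = 0.54
- independence: 0.93×0.90×0.80×0.70 = 0.469
- upper bound: 0.70

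For four rates of 90%:

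- no assumption: 4×0.90 − 3 = 0.60
- nested in histology: 3×0.90 − 2×0.90 = 0.90
- independence: 0.90⁴ = 0.656
- upper bound: 0.90

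| Assumed rates | Lower, no assumption | Independence | Lower, nested | Upper |
|---|---|---|---|---|
| 93/90/80/70% | 33% | 47% | 54% | 70% |
| 90/90/90/90% | 60% | 66% | 90% | 90% |

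**4. In patients.** With 250 biopsied and the first set of rates, the nested range runs from 0.54×250 = 135 to 0.70×250 = 175 patients. The same four published rates would fit either end.

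**5. Precision of a joint rate at n = 250.** The full width of the Wilson 95% interval is 2z·√(p(1−p)/n + z²/(4n²)) / (1 + z²/n), with z = 1.96.

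- p = 0.50: 12.3 points
- p = 0.60: 12.1 points
- p = 0.70: 11.3 points

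Section 5 names the width of the interval as the evaluated parameter, so its 10% is read here as full width. A joint rate of 50–70% would exceed that by one to two points.

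**The case against.** The strongest objection is that nothing is lost. Figure 1 names one evaluation form for pathology, NGS, IHC and immunology, and adequacy has a common denominator. The joint rate is then one cross-tabulation away, and a cross-tabulation is something that a statistical analysis plan may supply. This stands in part. A reader might infer that the trial cannot say in how many patients one biopsy served all examinations; the documents do not support that. But the endpoints and the meaning of feasibility are fixed in protocol section 2, and the mismatch with the objective lies there.

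A reader might also infer that every endpoint is an adequacy rate. Section 2.3 contradicts this, since it lists safety, predictive factors and accuracy for complex classification.

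Next, the objective does not literally say that all examinations must succeed in the same patient. Section 7 speaks of sample quality for classification by IHC, NGS and immunology, and per-examination rates describe that to some extent. The combined reading is the natural one for a complex classification, but it is a reading.

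Finally, the lowest bounds are extreme. Reaching 33% or 60% needs failures that never overlap, so that a patient who fails histology passes everything else. All examinations use the same tissue, and section 4.1.1 names necrotic or cystic material as a cause of inadequate samples. Positive dependence is likely, which makes independence doubtful too. If failures were fully nested, the joint rate would equal the lowest single rate, which is reported anyway. This stands, and is why the nested range is given beside the unrestricted one.

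**Conclusion.** The gap is real: no endpoint defines joint adequacy, the protocol's own feasibility measure does not touch the examinations, and the accuracy endpoint does not fill the hole. It is a mismatch between objective and endpoints, not a calculation error. The primary endpoint remains valid.

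The size cannot be fixed from the documents. With assumed rates of 93/90/80/70%, four separate rates leave the joint rate uncertain over 16 points (54–70%) if histology failure implies failure of the rest, and over 37 points (33–70%) with no assumption. With four rates of 90%, the nested case leaves no uncertainty, and the unrestricted range is 60–90%. It would go too far to conclude that the joint rate will be much lower than the separate ones: that depends on how failures overlap, which the trial can observe and should report.

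**What to change.** In sections 2.2 and 2.4, add a secondary endpoint: the proportion of patients who underwent TCB whose sample was adequate for every examination requested in that patient, with 95% CI. State that the conclusion on feasibility of complex classification rests on this rate.

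Report beside it the proportion adequate for all four examinations among patients in whom all four were requested. Section 4.2.2 describes IHC as done on indication, so an all-four rate over all biopsied patients would count an examination not requested as an inadequate sample. The definition should also say that an examination left out for lack of tissue counts as inadequate, so that such failures do not disappear as not requested.

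Keep the primary endpoint and the sample size.

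The cost is small: the proportions come from results due on the existing form. The protocol does not show the form's fields, so check that it records which examinations were requested. Over the same patients the joint rate can be no higher than the lowest single rate, so the headline may be less favourable. At n = 250 a joint rate of 50–70% has a 95% CI about 11–12 points wide, slightly above the 10-point target, and the interval is wider still for the subset with all four requested if that subset is smaller than 250.

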1. BACKGROUND AND RATIONALE

Image-guided diagnostic interventions are valuable tools in gynecologic oncology clinical practice. Several procedures are available, including core needle (tru-cut) biopsy (TCB) and fine needle aspiration biopsy (FNAB).

The purpose of performing biopsies in gynecologic practice is to obtain a representative tissue sample for a valid morphological examination. Biopsies are particularly useful for patients who are deemed unsuitable for more invasive interventions, and accelerate the process from diagnosis to therapy without the need for a period of recovery [1, 2]. In addition, in the era of personalized medicine, biopsies of gynecological cancers, either from primary, recurrent or progressive disease, have become important for characterizing the cellular pathways of the disease and to plan subsequent targeted therapy [3].

Tru-cut biopsy (TCB) is a minimally invasive method to obtain an adequate sample from the lesion and hence tailor the subsequent management avoiding unnecessary surgery. In gynecologic oncology, this technique is predominantly used in advanced ovarian cancers if primary cytoreductive surgery with no residual disease is not feasible and for patients indicated for neoadjuvant chemotherapy. Furthermore, it is useful to verify recurrent disease [4] and can be used in cases with tumors of presumed non-gynecologic origin that, in the pelvis, are mostly metastases derived from the gastrointestinal tract or breast cancer [5]. TCB can be used in combination with subjective ultrasound (US) assessment or with the assessment of different neoplasias in the adnexa (ADNEX) model to evaluate the nature of the majority of the pelvic tumor [6].

The Gynecologic Oncology Centre of the General University Hospital in Prague was among the first centers to start using TCB. Also, one of the largest retrospective studies published on this topic was done in our center. In the previous study, 190 patients were enrolled, and an adequate sample was obtained in more than 93% of all cases. In patients indicated for primary surgery or secondary debulking surgery, less than 2% of tru-cut biopsies did not coincide with the final histologic diagnoses. Regarding safety, only two bleeding complications, which were resolved by surgery, were recorded [7].

The samples obtained by TCB using an appropriate thick needle is usually sufficient for histopathological examination, immunohistochemistry (IHC), and next-generation sequencing (NGS). Although there is not yet strong evidence to show whether thick needle specimens are sufficient for the assessment of the tumor microenvironment based on immune monitoring, the available data are promising [8]. By contrast, FNAB only permits cytological examination with several crucial limitations to establish the final diagnosis [9, 10].

Modern examination methods (IHC, NGS, immunology) can give new information about the tumor's characteristics that can substantially affect the clinical prognosis and efficacy of different types of targeted treatment. Now, de novo biopsy in cases of disease recurrence or progression is strongly recommended because it can reveal the alterations of these characteristics that occur during the course of treatment and improve the therapeutic strategies. In ovarian cancer, high temporal heterogeneity of tumor biopsies has been demonstrated, with a significant clinical impact [11].

TCB can be considered the smartest way to histopathologically verify a gynecologic malignancy because it is minimally invasive, is performed in an outpatient basis, and is well tolerable with a low complication rate. Furthermore, TCB has an excellent cost–benefit ratio.

2. ENDPOINTS

2.1. Primary endpoint

The primary endpoint is the adequacy of samples obtained by TCB for histopathological diagnosis at the Gynecologic Oncology Center of the General University Hospital in 3 years.

2.2. Secondary endpoint

The secondary endpoint is the adequacy of samples obtained by TCB for next generation sequencing, immunohistochemistry, and immunologic examination.

2.3. Additional endpoints

1. To evaluate which factors affect the primary and secondary endpoint, including:
 - a. tumor origin
 - b. size of the tumor
 - c. presence of ascites
 - d. body mass index (BMI)
 - e. biopsy site
 - f. biopsy approach transvaginal, transrectal vs. transabdominal
 - g. disease status – the first diagnosis, the first and other recurrence or progression
 - h. previous treatment modality – chemotherapy, anti-angiogenic therapy, PARP inhibitor therapy, hormonal therapy, or radiotherapy
2. To evaluate the overall safety of TCB
3. To evaluate the overall accuracy of TCB for complex classification of pelvic and abdominal tumors

2.4. Definitions of endpoints

The feasibility of TCB will be calculated as the proportion of patients in whom TCB was performed among all patients enrolled in the study.

Adequacy is defined as the proportion of patients in whom an adequate sample was obtained for a particular examination from among those patients who underwent TCB.

Accuracy will only be evaluated in patients in whom an adequate sample was obtained by TCB who underwent surgery with biopsy. Accuracy is defined as the concordance between the examination of samples obtained by TCB and the results of surgery with TCB to the final histopathology. The outcome of the final histopathological examination will be considered the reference standard.

For accuracy and adequacy, the impact of selected variables (e.g., approach, number of biopsies, and target lesion size) will be assessed in a multivariable analysis.

Safety is defined as the rate of complications related to TCB, including events occurring during the procedure, events within 24 hours after the procedure (early events), and events within 30 days of the procedure (late events).

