5. STATISTICAL ANALYSIS

The power analysis was computed for adequacy/feasibility of immunological examination based on published data and a pilot study for samples obtained by TCB.

The sample size analysis was calculated for adequacy of samples obtained by TCB for histopathological diagnosis. The calculation was computed under the assumption of sample adequacy between 50-90%. The evaluated parameter was the width of 95% confidence interval for the proportion of adequate sample (Table 1-2).

With the expected adequacy of the samples in the range of 70-90%, we plan to enroll at minimum 250 subjects, in order to achieve confidence interval of $\leq 10\%$.

The analysis was computed using PASS 16 Power Analysis and Sample Size Software (2018) NCSS, LLC. Kaysville, Utah, USA, ncss.com/software/pass, by Institute of Biostatistics and Analyses (Faculty of Medicine, Masaryk University, Brno). [32, 33]

Standard descriptive statistics will be applied for the exploratory analysis, including absolute and relative frequencies for categorical variables and medians with 5th–95th percentiles and/or means with standard deviations or confidence intervals (95%) of point estimates. The statistical significance of differences in categorical variables will be assessed using the maximum likelihood chi-square test. The accuracy, adequacy, and safety will be assessed by performing receiver operator characteristic (ROC) curve analysis, after selecting appropriate predictors, and with a standard set of descriptive statistics alongside confidence intervals related to the individual predictors (area under the curve, sensitivity, specificity, positive and negative predictive value, overall accuracy).

Statistical analyses will be performed using SPSS 24.0.0.0 (IBM Corporation, 2015) statistical software.

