7. EXPECTED OUTCOMES

This prospective study is to our knowledge the first study registered on www.clinicaltrials.gov designed to prospectively evaluate the quality of samples obtained by TCB for comprehensive classification of pelvic and abdominal malignant tumors by IHC, NGS, and immunological evaluation, and allowing evaluation based on location, size, and other factors. Our study is also expected to confirm the known feasibility and safety of TCB, and demonstrate its high adequacy and accuracy. The findings should also provide an update to the promising results of a previous retrospective analysis of TCB in a larger study population.

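### Section 2.4 promises a multivariable analysis of accuracy, but the protocol's own discordance rate implies fewer than 5 discordant cases, so the model would often not be estimable

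*Protocol*

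**What the plan says.** Section 2.4 of the protocol states, for accuracy and adequacy alike, that "the impact of selected variables (e.g., approach, number of biopsies, and target lesion size) will be assessed in a multivariable analysis". It limits accuracy to patients who have both an adequate tru-cut sample and surgery, and takes the final histopathology as the reference standard.

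Section 1 reports the centre's earlier retrospective series of 190 patients: "an adequate sample was obtained in more than 93% of all cases", and, among patients going to primary or secondary debulking surgery, "less than 2% of tru-cut biopsies did not coincide with the final histologic diagnoses".

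Section 5 bases the sample size on the precision of one proportion, adequacy for histopathology: "With the expected adequacy of the samples in the range of 70-90" per cent, "we plan to enroll at minimum 250 subjects". It gives no expected number of operated patients and no expected number of discordances.

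**The concern.** A regression for accuracy draws its information from the discordant cases. If there are none, there is nothing to model. If there are one or two, they will often all fall in one category of a predictor such as approach. The maximum likelihood estimate for that predictor is then infinite, and its Wald interval and p-value have no meaning.

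At stake is a stated analysis of an additional endpoint. It might produce no result, or it might produce a table of factor effects that reflects only where two or three cases happened to fall. The choice of variables in a statistical analysis plan cannot cure this, because the shortage is of events.

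**Working it through.** **Inputs**

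- N = 250 (Section 5).
- Adequacy 93%, the historical lower figure (Section 1); planning range 70 to 90% (Section 5).
- Discordance 2%, the historical upper figure (Section 1).
- Share of adequate patients who have surgery: not stated. Assumed 100%, 50% and 30%. Section 1 says that the technique is used mainly where complete primary cytoreduction is not feasible, so 100% is a generous limit.

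**The plan's own figure.** The 250 comes from the width of a 95% interval for adequacy. The Wald width is 2 × 1.96 × √(p(1−p)/250), which is 9.9% at p = 0.80 and 11.4% at p = 0.70. The shortfall against the 10% target at 70% is a separate matter. The plan has no corresponding figure for accuracy to reproduce.

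**Expected discordances** = 250 × adequacy × surgery share × 0.02

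- 100% surgery: 250 × 0.93 × 1.0 × 0.02 = 4.65
- 50% surgery: 250 × 0.93 × 0.5 × 0.02 = 2.3
- 30% surgery: 250 × 0.93 × 0.3 × 0.02 = 1.4

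The planning range does not help, because lower adequacy shrinks the accuracy denominator. At 90% adequacy and full surgery, 225 × 0.02 = 4.5; at 70%, 175 × 0.02 = 3.5.

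**A floor for failure, from approach alone.** Assume that approach is split 50/50 and has no true effect. Its coefficient is not finite if either category has no discordance. The probability is 2 × 0.99^n − 0.98^n, where 0.98^n is the chance of no discordance at all.

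| Operated (share) | No discordance, 0.98^n | Not estimable, approach alone |
|---|---|---|
| 232 (100%) | 0.9% | 2 × 0.0971 − 0.0092 = 18.5% |
| 116 (50%) | 9.6% | 2 × 0.3117 − 0.0960 = 52.7% |
| 70 (30%) | 24.3% | 2 × 0.4948 − 0.2431 = 74.7% |

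**All three named variables.** Separation was checked by linear programming in simulated trials with no true effects. Approach had two categories, number of biopsies was one linear term and size was a normal variable (3 parameters). The share of trials with no event or with separation was:

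- 100% surgery: about 22 to 29%
- 50% surgery: about 60%
- 30% surgery: about 76 to 80%

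The spread reflects the assumed predictor distributions. A repeat with 2,000 datasets per setting and two such distributions gave slightly lower figures: 21 to 22%, 53 to 58% and 75 to 78%. With approach and number of biopsies in three categories each (5 parameters), failure was 88% at 232 operated and 97% at 100. At 1% discordance the 3-parameter model failed in 55% of trials at 232 operated and 88% at 100.

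**Adequacy, for comparison.** Inadequate samples number 250 × 0.07 = 17.5 at the historical rate, and 25 to 75 at 90 to 70% adequacy. With 3 parameters, 17.5 / 3 = 5.8 events per parameter. No simulated trial separated at any of these rates.

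**The case against.** **The discordance rate may not carry over.** The figure below 2% is retrospective and concerns histologic diagnosis, while Section 2.3 speaks of accuracy for complex classification, for which no rate is given. This stands as a limit on the size. However, Section 2.4 makes the final histopathology the reference standard, so the histologic rate is the closest one in the document. To reach the 17.5 events available for adequacy, discordance would have to be 17.5 / 232.5 = 7.5% with everyone operated on, or 17.5 / 116.25 = 15% with half. That is about four to eight times the centre's figure.

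**The method is not fixed.** The protocol does not name the regression method, and estimator and variable choice can properly be left to an analysis plan. This is fair. A penalised method would return finite numbers, but with one to five events it would still say very little about three factors.

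**The surgery share is unknown.** This is true, and it is why a range is shown. Even the most favourable end fails in more than one trial in five.

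**What a reader might also infer.** Section 2.3 sets out "To evaluate which factors affect the primary and secondary endpoint, including" eight listed items, a to h. One might conclude that a model with all of them is planned for adequacy and would usually separate. The documents do not support that. Section 2.4 speaks only of selected variables, and Section 2.3 does not put all eight in one model. At 93% adequacy the simulated separation rate for such a model runs from about 1% (8 parameters) to 91% (21 parameters), depending entirely on assumed coding. Nor does Section 7, "allowing evaluation based on location, size, and other factors", promise adjusted effects or an accuracy model; proportions by subgroup would meet it. No adequacy rates are given for sequencing, immunohistochemistry or immunology, so sparse events cannot be assumed there.

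**Conclusion.** The concern holds for accuracy. On the protocol's own rates, fewer than 5 discordances are expected at best, and about 1.4 to 2.3 if 30 to 50% of adequate patients have surgery. The three-variable model would then be unusable in roughly a fifth to four fifths of trials. This rests on a discordance rate of 2% (the document says less, which would make matters worse), on an assumed surgery share and on assumed predictor distributions. The closed-form floor of 18.5 to 74.7% needs only the 50/50 split in approach.

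It does not hold as a general objection to modelling histopathological adequacy. A model with the few named variables can be fitted, though about 6 events per parameter at 93% adequacy is thin. The primary endpoint is a single proportion and is not affected. The change should be made, but it concerns an additional endpoint only.

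**What to change.** In Section 2.4, delete accuracy from the sentence that promises a multivariable analysis. State instead that concordance will be reported as a proportion with an exact 95% confidence interval, that each discordant case will be listed with its approach, number of biopsies and lesion size, and that concordance will be described by factor without a model. Section 5 also names accuracy among the outcomes assessed after choosing predictors; its wording should be made to agree.

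For histopathological adequacy the sentence can stay, with a note that the number of model parameters will be kept small relative to the inadequate samples observed. No change to Section 7 is needed.

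The cost is wording only, with no extra patients or data. The study gives up adjusted factor effects for accuracy, which its expected event count could not have supported.
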